#### 17.3.1 Derivations

• BMI  $(kg/m^2) = [Weight (kg)/(Height (cm)/100)^2].$ 

### 17.4 Laboratory Evaluations

Clinical laboratory results (hematology, clinical chemistry, urinalysis, and lipid profile) will be summarized (see **Section 8.1** Statistical Summaries, Tests and Confidence Intervals for a description of statistics to be reported) at each visit.

### 18. EXPLORATORY ANALYSES – EFFECTIVENESS

The exploratory analyses will be performed using the EAS population.

### **18.1** Exploratory Analysis Variables

The exploratory objective is to evaluate the effectiveness achieved with daily SC metreleptin treatment in patients with congenital or acquired generalized lipodystrophy. The exploratory effectiveness variables are:

- hemoglobin A1c (HbA1c)
- fasting plasma glucose
- triglycerides
- leptin/metreleptin concentration

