3.4 Exploratory Objectives

Exploratory Objective: Outcome Measure:

Evaluate the efficacy achieved with daily SC metreleptin treatment in patients with congenital or acquired generalized lipodystrophy.

Change from baseline in HbA1c and fasting triglycerides over time.

Confidential Page 19 of 60

[figure not shown]

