6. STUDY PROCEDURES

6.1 Schedule of Assessments

Study procedures are summarized in Table 1. Detailed descriptions of the efficacy, PK, and safety procedures to be conducted during this study are provided in the following sections.

Confidential Page 26 of 60

Table 1: Schedule of Study Assessments

Visit Number	SCREENING 1	2	3	4	5	6	7	8	9	10	11	12	FOR DETAILS, SEE PROTOCOL SECTION:
MONTH	-1	0	1	2	4	6	9	12	18	24	30	36	
WINDOW (DAYS)	-28 то 0	±0	±7	±7	±7	±7	±7	±14	±14	±14	±14	±14	
PROCEDURE													
Informed Consent and Assent	X												
Demographics	X												
Medical/Surgical History	X	X											
Inclusion/Exclusion criteria	X	X											
Physical Examination,	X							X		X		X	
Vital Signs/ Weight/ Height ^a	X	X	X	X	X	X	X	X	X	X	X	X	
Serum or Urine Pregnancy Test ^b	X	X	X	X	X	X	X	X	X	X	X	X	
Fasting Samples for Hematology & Clinical Chemistry	X	X				X		X	X	X		X	
HbA1c, Lipids, Fasting Glucose	X	X	X	X	X	X	X	X	X	X	X	X	
Samples for Antibody and Leptin Measurements ^c		X	X	X	X	X	X	X	X	X	X	X	

Confidential Page 27 of 60

A NOVELION THERAPEUTICS COMPANY

VISIT NUMBER	SCREENING 1	2	3	4	5	6	7	8	9	10	11	12	FOR DETAILS, SEE PROTOCOL SECTION:
MONTH	-1	0	1	2	4	6	9	12	18	24	30	36	
WINDOW (DAYS)	-28 то 0	±0	±7	±7	±7	±7	±7	±14	±14	±14	±14	±14	
PROCEDURE													
Urinalysis	X							X		X		X	
Study Medication Administration First Dose		X											
Adverse Events, including SAEs and AESI		Continuous Monitoring											
Concomitant use of Lipid-Lowering, Antidiabetic and Immunomodulatory Agents	X	X	X	X	X	X	X	X	X	X	X	X	

- a For all pediatric patients (≤18 years of age), a pubertal development assessment should also be conducted at Screening and Months 12, 24, and 36.
- b A serum or urine pregnancy test (βhCG) should be completed for all female patients of child-bearing potential, unless the patient has had a hysterectomy.
- c Samples for antibody measurement should be taken before administering metreleptin at each study visit in order to minimize high levels of metreleptin in the samples, which could interfere with antibody testing.

Confidential Page 28 of 60

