7.4.1 Collection of Samples for Measurement of Leptin

Blood samples for the measurement of leptin will be collected at the times specified in the Study Plan (Table 1). The centralized laboratory will provide specific instructions for collection, processing, packaging, and shipping of all samples.

Additional safety samples for measurement of leptin will be collected if clinically indicated (e.g., loss of response to MYALEPT, or if patient develops a severe infection and/or sepsis), or at the discretion of the Investigator. The date, time of collection, and results (values, units, and reference ranges) will be recorded on the appropriate eCRF.

Confidential Page 35 of 58

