7.4.2 Determination of Leptin Concentration

Samples for determination of leptin concentration in plasma will be analyzed by a local laboratory using an appropriate bioanalytical method. Full details of the analytical methods used will be described in a separate bioanalytical report.

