#### 18.2 Exploratory Analysis Description, Derivations, and Definitions

Exploratory variables will be summarized using descriptive statistics (see **Section 8.1** Statistical Summaries, Tests and Confidence Intervals) and results will be presented as described below below:

- by visit
- as absolute change from baseline and percent change from baseline at each visit

HbA1c, fasting plasma glucose, and triglycerides will also be summarized by clinically relevant categories at each visit:

- $\circ$  hbA1c (<8%, >=8%)
- o fasting plasma glucose (<70 mg/dL, >=70 mg/dL and <=100 mg/dL, <100 mg/dL)

Document:	Statistical Analysis Plan: AEGR-734-401: A 36-Month, Multicenter, C	Open Label Phase 4 Study to Ev	aluate the
	Immunogenicity of Daily SC Metreleptin Treatment in Patients with	Generalized Lipodystrophy	
Author:	[name], [name], [name], [name]	Version Number:	2.1
		Version Date:	131// 1202/

o triglycerides (<500 mg/dl, >=500 mg/dl).

See Section 8.1 Statistical Summaries, Tests and Confidence Intervals for a description of statistics to be reported.

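### Leptin/metreleptin concentration measures exposure, not effectiveness: its percent change from a very low baseline is unstable, and it is not set beside the antibody results it could help interpret

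*SAP*

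**What the plan says.** SAP 18.1 opens its list with "The exploratory effectiveness variables are" and names HbA1c, fasting plasma glucose, triglycerides and "leptin/metreleptin concentration". SAP 18.2 presents all four by visit and "as absolute change from baseline and percent change from baseline at each visit". Only three go further: "HbA1c, fasting plasma glucose, and triglycerides will also be summarized by clinically relevant categories at each visit". By-visit values and the two change summaries are therefore the whole planned analysis of concentration.

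The protocol treats the measure differently. Section 3.4 gives the exploratory outcome as "Change from baseline in HbA1c and fasting triglycerides over time", and section 10.4 names the same two variables for efficacy. Section 7.1 adds fasting glucose to the efficacy assessments, but not leptin. Leptin is under Pharmacokinetics (7.4), which says it will be measured without formal pharmacokinetic analysis.

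The protocol's Table 1 puts antibody and leptin samples on one row, Visits 2 to 12. Footnote c asks for antibody samples before that day's dose, to limit high drug levels "which could interfere with antibody testing". SAP 15.2 calls a sample ADA positive if binding is detected at the minimum required dilution (1:10) and negative otherwise. Under protocol 7.3.1 and SAP 15.1, the cell-based neutralizing (NAb) and receptor-blocking (RB) assays apply only to ADA-positive samples.

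On laboratory and matrix, protocol 7.4.1 says: "The centralized laboratory will provide specific instructions for collection, processing, packaging, and shipping of all samples". Section 7.4.2 says: "Samples for determination of leptin concentration in plasma will be analyzed by a local laboratory using an appropriate bioanalytical method". The blood-tube table in section 7 (Table 2) gives antibody and leptin one shared line with a gold SST tube, a serum-separator type.

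**The concern.** Two things look wrong.

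The first is classification and scale. The SAP's own label allows that the assay measures administered metreleptin as well as endogenous leptin. A rise after the first dose then shows that drug is present, not that metabolic control improved. Percent change makes this worse in a population with leptin deficiency, because the denominator is expected to be small. SAP 8.1 and 8.2 contain no rule for a baseline below quantification.

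The second is a missed use of data that bears on the primary result. The protocol identifies a mechanism that could affect the antibody assay, and it schedules a drug-level measurement at the same visits. The visible SAP never brings the two together. If a negative were caused by drug in the sample, the patient would be counted ADA negative at that visit, and the sample would also receive no NAb or RB result.

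**Working it through.** No figure in the plan is at issue. The check traces the variable through the documents and then illustrates size. The documents give no leptin levels, half-life or drug-tolerance limit, so every concentration below is an assumption.

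**1. What the change from baseline measures.**
- Baseline: drawn before the first dose (protocol 6.2.2), so endogenous leptin only.
- Population: leptin deficient from loss of adipose tissue (protocol 2.3).
- Later visits: patients are on daily injections unless treatment has stopped, so samples can contain drug.

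On treatment, the change is therefore endogenous leptin plus residual drug, minus a small endogenous value.

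**2. Behaviour of the percent change.** Percent change = 100 × (post − baseline) / baseline.

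| Assumed baseline (ng/mL) | Post 5: absolute | Post 5: percent | Post 20: absolute | Post 20: percent |
|---|---|---|---|---|
| 0.1 | 4.9 | +4900% | 19.9 | +19900% |
| 0.5 | 4.5 | +900% | 19.5 | +3900% |
| 1 | 4 | +400% | 19 | +1900% |
| 2 | 3 | +150% | 18 | +900% |
| 4 | 1 | +25% | 16 | +400% |

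For a post-dose level of 20, the absolute change varies by a factor of 19.9/16 = 1.2, while the percent change varies by 19900/400 = 50. The percent column mostly ranks patients by denominator. At a zero baseline it is undefined, so the most deficient patients leave that column, though not the by-visit or absolute summaries.

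**3. What masked positives would cost, if there were any.** Assume 10 patients, 8 truly ADA positive at a visit. Exact 90% Clopper-Pearson limits are the 5% point of Beta(x, n − x + 1) and the 95% point of Beta(x + 1, n − x).

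| Masked | Observed | Exact 90% CI |
|---|---|---|
| 0 | 8/10 | 0.49 to 0.96 |
| 1 | 7/10 | 0.39 to 0.91 |
| 2 | 6/10 | 0.30 to 0.85 |
| 3 | 5/10 | 0.22 to 0.78 |

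The table shows sensitivity to masking. It is not evidence that masking occurs.

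**4. What the sensitivity summary would show.** Take 6/10 observed, with two of the four negatives above the tolerance limit. Treating those two as inconclusive gives 6/8 = 0.75 (exact 90% CI 0.40 to 0.95). Counting them as negative gives 6/10 and as positive gives 8/10. If no negative exceeds the limit, the summary equals the main result and the question is closed.

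**5. Whether the SAP already pairs the two.** Sections 15.1, 15.2, 16, 17.1 and 18 and the visible change note contain no link between an ADA, NAb or RB result and the concurrent concentration.

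**The case against.** The strongest reply has four parts.

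- **Interference is already mitigated.** Footnote c says only that interference could occur, gives no direction, and requires pre-dose sampling; protocol 6.3 repeats this for all visit procedures. With an assumed half-life of 3 to 6 h, the fraction left is 2^(−12/3) to 2^(−12/6), about 6% to 25%, at 12 h, and 2^(−24/3) to 2^(−24/6), about 0.4% to 6%, at 24 h. This stands. A reader might infer that by-visit positivity is biased downward. The documents do not support that: they give no tolerance limit, observed level or false-negative rate. What remains is that footnote c fixes the order on the day and not the time since last dose, and that the unscheduled samples in protocol 7.3.1 carry no stated pre-dose rule.
- **A joint display is planned.** Protocol 10.5 plots titers, neutralizing activity and metreleptin exposure per patient over time. This stands in part. Exposure may mean dose, and the SAP text specifies no such plot. SAP 9 and 15 allow extra figures, and the table and figure shells are not in these documents, so a concentration display cannot be excluded.
- **The stakes in SAP 18 are low.** The analysis is exploratory and descriptive, by-visit values and absolute change are also planned, and a row labelled as concentration is unlikely to be mistaken for clinical benefit. This stands and limits the severity. The SAP's modification history also logs the addition, although SAP 4.3 declares no change from the protocol.
- **The protocol gives concentration no checking role.** True: this is a missed use of collected data, not a broken commitment.

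A reader might also infer that leptin was assayed by different methods across about ten centers, or that dose times were never recorded. Neither is shown. Section 7.4.2 speaks of one local laboratory and one method. Protocol 9.5 requires dose and duration to be recorded, and the case report form is not available here.

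**Conclusion.** The point holds as a cheap improvement. Concentration is an exposure measure placed under effectiveness, and its percent change is a poor summary for leptin-deficient patients. Both follow from the text; only the sizes in the tables are assumed.

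On the primary analysis, the claim goes no further than this: the protocol names a possible interference, a concentration is scheduled with each antibody sample, and the visible SAP classifies negatives without looking at it. Whether any negative is affected cannot be judged without the assay's drug tolerance and the observed concentrations. With about ten patients, each reclassified sample moves a by-visit proportion by about 0.1, so the check is worth making even if it finds nothing.

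The laboratory and matrix statements in protocol 7.4.1, 7.4.2 and Table 2 do not agree. They must be reconciled before a concentration is paired with an antibody result, because a plasma sample would not have come from the shared serum tube.

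**What to change.** 1. Move leptin/metreleptin concentration from SAP 18 to exposure (SAP 14). Keep by-visit values and absolute change, drop percent change, and state how non-quantifiable values are shown.
2. List or plot concentration beside each ADA, NAb and RB result, by patient and visit. This gives effect to the exposure plot in protocol 10.5.
3. In SAP 15.2, add one sensitivity summary of ADA positivity in which ADA-negative samples above the validated drug tolerance are inconclusive. The limit must come from the assay validation report and be fixed before the paired data are examined.
4. State which matrix and laboratory were used for leptin, and reconcile protocol 7.4.1, 7.4.2 and Table 2. If time of last dose was not captured, report that as a limitation.

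The SAP change note contains entries dated after database lock, so step 3 should be labelled post hoc if done now, and new data fields or a change of laboratory are no longer realistic. Steps 1 to 3 use concentrations the protocol already schedules. The cost is revised wording, one listing or figure and one summary row. The downside is that a few ADA-negative results may become inconclusive, which widens intervals that are already wide.

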#### 18.2 Exploratory Analysis Description, Derivations, and Definitions

Exploratory variables will be summarized using descriptive statistics (see **Section 8.1** Statistical Summaries, Tests and Confidence Intervals) and results will be presented as described below below:

- by visit
- as absolute change from baseline and percent change from baseline at each visit

HbA1c, fasting plasma glucose, and triglycerides will also be summarized by clinically relevant categories at each visit:

- $\circ$  hbA1c (<8%, >=8%)
- o fasting plasma glucose (<70 mg/dL, >=70 mg/dL and <=100 mg/dL, <100 mg/dL)

Document:	Statistical Analysis Plan: AEGR-734-401: A 36-Month, Multicenter, C	Open Label Phase 4 Study to Ev	aluate the
	Immunogenicity of Daily SC Metreleptin Treatment in Patients with	Generalized Lipodystrophy	
Author:	[name], [name], [name], [name]	Version Number:	2.1
		Version Date:	131// 1202/

o triglycerides (<500 mg/dl, >=500 mg/dl).

See Section 8.1 Statistical Summaries, Tests and Confidence Intervals for a description of statistics to be reported.

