10.5 Methods for Statistical Analyses

There will be no hypothesis testing. All data will be summarized by descriptive statistics and/or listings. In general, continuous variables will be summarized by n, mean, SD, median, min and max. Number of patients and percentage of patients in a category will be provided.

Descriptive statistics will be provided for immunogenicity variables (Section 10.4). The maximum antibody titer (anti-metreleptin or anti-HuL) during a visit will be summarized by visit. Categorization of *in vitro* neutralizing activity as assessed by cell-based assay will be summarized across visits; the rate of Category D and E *in vitro* neutralizing activity with 90% and 80% exact confidence intervals will be computed. The results are reported as percent inhibition and 80% inhibition is currently utilized as the neutralizing antibody threshold. activity Results for *in vitro* neutralizing activity will be summarized across visits; however, there will be no formal comparison of the 2 assay methods for the detection and relative potency of Category D or E *in vitro* neutralizing activity.

Maximum antibody titers, neutralizing activities detected by both methods, and metreleptin exposure for each patient will be plotted over time. Maximum antibody

Confidential Page 47 of 58

titers, neutralizing activities detected by both methods, and any associated clinical events (i.e., loss of efficacy or AE) will be summarized.

All AEs will be coded using the Medical Dictionary for Regulatory Activities (MedDRA). The number and percentage of patients who experienced at least 1 AE will be summarized by system organ class and preferred term. AEs will be summarized by relationship to the study medication and by severity. Deaths, SAEs, AESIs, and AEs leading to discontinuation will be tabulated and/or listed. SAEs, AESIs and AEs leading to discontinuation will be summarized respectively by peak antibody titers (antimetreleptin, anti-HuL) and by *in vitro* neutralizing activity categories or percent inhibition.

Clinical laboratory results (hematology, chemistry, and urinalysis), and vital signs results will be summarized using descriptive statistics for each visit.

Change from baseline in HbA1c and percent change from baseline in fasting triglycerides will be summarized for each visit by overall patient population, by peak antibody titers (anti-metreleptin, anti HuL), and by *in vitro* neutralizing activity categories or percent inhibition , respectively.

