### 15.2 Primary Analysis Description, Derivations, and Definitions

The presence of anti-drug antibodies will be screened using an ADA binding assay, which detects antibodies to both Metreleptin and HuL, and reported as follows:

- Positive/negative for ADA binding by study visit. Positive ADA is defined as ADA binding detected at MRD (1:10 dilution factor). Both 90% and 80% two-sided Clopper-Pearson exact CIs will be presented.
- ADA binding by study visit and titer (negative [no ADA binding detected at MRD], 1:10, 1:50, 1:250, 1:1250, 1:6250, 1:31250). Dilution factors greater than 1:31250 will not be examined.
- Ever ADA positive and time to ADA positivity. Time to ADA positive result (months) = [((date of first ADA positive result date of baseline visit) + 1)/30.4].
- Peak ADA (defined as the measurement which detects ADA binding activity at the largest dilution factor) and time to peak ADA. Time to peak ADA (months) = [((date of peak ADA date of baseline visit) + 1)/30.4].

In vitro NAb activity will be measured in a cell-based assay and categorized into A, B, C, D and E categories based on titer. Categorization will be performed by IQVIA Data Management and the resulting derived data will be provided to IQVIA RWE Biostatistics. Positive/negative for NAb activity, high positive NAb activity, and NAb titer categories will be presented by study visit along with two-sided 90% and 80% Clopper-Pearson exact CIs. The titer categories are defined as follows:

- If no activity is detected upon initial testing (1:80 dilution factor) with the cell-based assay, the result is reported as category A.
- If activity is detected at the initial test concentration, the sample is retested at the same concentration (1:80 dilution factor). If no activity is detected on retest, the initial result is attributed to assay noise, and the sample is reported as category B.
- If activity is detected on both tests at MRD, the sample is diluted and retested until activity is no longer detected. Depending on the number of dilutions required to dilute NAb activity below the detectable threshold, the result is reported as follows:
  - o If no activity is detected at 1:800 dilution factor, then category C
  - o If no activity is detected at 1:8000 dilution factor, then category D
  - o If activity is detected at 1:8000 dilution factor, then category E. Dilution factors greater than 1:8000 will not be examined.

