Positive NAb activity will be defined as a titer category C, D, or E result. High positive NAb activity will be defined as a a titer category D or E result. Category D and E results are considered to represent

Document: Statistical Analysis Plan: AEGR-734-401: A 36-Month, Multicenter, Open Label Phase 4 Study to Evaluate the

Immunogenicity of Daily SC Metreleptin Treatment in Patients with Generalized Lipodystrophy

Author: [name], [name], [name], [name] Version Number: 2.1

high potency NAb activity. The clinical relevance of NAb activity results in any category has not been determined, and is a topic of current investigation. The following information will be summarized:

- Ever NAb positive and time to NAb positivity. Time to NAb positivity (months) = [((date of first NAb positive result date of baseline visit) + 1)/30.4].
- Ever high NAb positive and time to high NAb positivity. Time to high NAb positivity (months) = [((date of first hight NAb positive result date of baseline visit) + 1)/30.4].
- Peak NAb (defined as the measurement which detects NAb activity at the largest dilution factor) and time to peak NAb. Time to peak NAb activity (months) = [((date of peak NAb date of baseline visit) + 1)/30.4].

RB activity of anti-metreleptin/anti-HuL will be assessed by ECLIA receptor blocking assay and reported as follows:

- Positive/negative for RB activity by study visit. Positive RB activity is defined as RB activity detected at MRD (1:6 dilution factor). Both 90% and 80% two-sided Exact CIs will be presented.
- RB activity by study visit and titer (negative [no RB activity detected at MRD], 1:6, 1:30, 1:300, 1:3000). Dilution factors greater than 1:3000 will not be examined.
- Percent inhibition at MRD by study visit
- Ever RB positive and time to RB positivity. Time to RB positivity (months) =  $[((date \ of \ first \ RB \ positive \ result date \ of \ baseline \ visit) + 1)/30.4].$
- Peak RB (defined as the measurement which detects RB activity at the largest dilution factor) and time to peak RB. Time to peak RB result (months) = [((date of peak RB date of baseline visit) + 1)/30.4].

See **Section 8.1** Statistical Summaries, Tests and Confidence Intervals for a description of statistics to be reported.

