#### 17.1 Adverse Events

Adverse Events (AEs) will be coded using the latest version of MedDRA, and summarized by SOC, preferred name, and intensity. Intensity is captured in the CRF. See **Section 8.1** Statistical Tests and Confidence Intervals for a description of summaries to be reported.

Adverse Events of Special Interest (AESIs) are defined as:

- The presence of Category D or E *in vitro* cell-based NAb activity (or the relevant corresponding test result from the ligand-binding method) to metreleptin
- Necrotizing pancreatitis
- Hepatic adverse events including potential drug induced liver injury (DILI)
- Severe hypoglycemia
- Severe hypersensitivity reactions
- New diagnoses of autoimmune disorders (for instance, autoimmune hepatitis, glomerulonephritis, lupus erythematosus, antiphospholipid antibody syndrome, rheumatoid arthritis)
- Autoimmune disease exacerbation
- Serious infection resulting in hospitalization
- All cancers (excluding non-melanoma skin cancer) by cancer type
- Exposed pregnancies and pregnancy outcomes.

TEAEs are defined as AEs that started or worsened in severity on or after the first dose of study medication. If it is unclear whether or not an AE is a TEAE due to partial dates, the worst case will be assumed (i.e., TEAE). See **Appendix 1** for handling of partial dates.

AEs, serious AEs (SAEs), AEs of special interest (AESIs), TEAEs, AEs possibly caused by metreleptin, and AEs leading to metreleptin discontinuation will be summarized by ADA positivity and titer, cell-based NAb positivity and titer, and RB positivity, titer, and quintile of percent

Document: Statistical Analysis Plan: AEGR-734-401: A 36-Month, Multicenter, Open Label Phase 4 Study to Evaluate the

Immunogenicity of Daily SC Metreleptin Treatment in Patients with Generalized Lipodystrophy

Author: [name], [name], [name], [name] Version Number: 2.1

inhibition. For each patient, only one event of each type will be selected to include in summary outputs. If a patient has multiple events the same type, the event with the highest severity level is selected. For patients with multiple events of the same type and severity, the event corresponding to the highest titer or percent inhibition level is selected. The corresponding titer and percent inhibition level are defined by the most recent measurement occurring prior to the event start date.

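### SAP 18.2 omits the protocol's HbA1c and triglyceride summaries by antibody status, and SAP 4.3 does not declare the departure

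*SAP*

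**What the plan says.** Protocol 10.5 states that change in HbA1c and percent change in fasting triglycerides "will be summarized for each visit by overall patient population, by peak antibody titers (anti-metreleptin, anti HuL"), and it adds neutralizing category or percent inhibition as further strata. For safety it states that "SAEs, AESIs and AEs leading to discontinuation will be summarized respectively by peak antibody titers", again with neutralizing category or percent inhibition. It also plans a figure in which maximum titers, neutralizing activity by both methods and "metreleptin exposure for each patient will be plotted over time".

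SAP 18.2 summarizes HbA1c, fasting plasma glucose, triglycerides and leptin/metreleptin concentration by visit and "as absolute change from baseline and percent change from baseline at each visit", and puts the first three into clinical categories at each visit. It names no antibody stratum. SAP 15.2 derives the peaks that would be needed, for example "Peak ADA (defined as the measurement which detects ADA binding activity at the largest dilution factor) and time to peak ADA" and "Peak RB (defined as the measurement which detects RB activity at the largest dilution factor) and time to peak RB", with a matching definition for the cell-based assay.

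SAP 17.1 tabulates AEs by ADA, NAb and RB status and says: "The corresponding titer and percent inhibition level are defined by the most recent measurement occurring prior to the event start date".

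SAP 4.3 declares that the analysis is unchanged from the protocol. SAP 2 says that the SAP's methods override the protocol's where the two differ.

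**The concern.** Protocol 3.3 asks for safety and tolerability in relation to antibody status. Among its outcomes it lists loss of response as assessed by HbA1c and serum triglycerides. Protocol 2.1 describes the postmarketing requirement as including an analysis of clinical events over time associated with binding or neutralizing antibodies. The stratified HbA1c and triglyceride summaries in protocol 10.5 are the planned output that speaks most directly to that question with measured values.

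If the visible SAP is followed, those summaries are not produced. Because SAP 2 gives the SAP precedence, the protocol text does not rescue them. Because SAP 4.3 declares no departure, a reader of the study report has no signal that a planned analysis was left out. What is at stake is a descriptive link between antibody status and metabolic control, and the accuracy of the SAP's own statement of departures.

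**Working it through.** No figure in the plan needs reproducing for this point. The check is a comparison of texts, followed by small counts to size the fix.

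1. **HbA1c and triglycerides by antibody status.** Protocol 10.5: each visit, overall, by peak titer, and by neutralizing category or percent inhibition. SAP 18.2: each visit and clinical category only. SAP 15.2 derives peak ADA, NAb and RB, but no visible SAP section crosses them with HbA1c or triglycerides. The visible change-note items of 16 December 2024 redefine the EAS, restrict the AE tables to TEAEs and revise the visit windows. None adds an antibody stratum to SAP 18. The analysis is absent from the visible text.

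2. **Do the AE tables fill the gap?** In part. Protocol 8.3.8 treats suspected loss of response as an AE of special interest, to be recorded in the eCRF with a neutralizing-activity sample. The AESI list in SAP 17.1, like the list in protocol 8.2, omits it. If it is recorded as an AE it can still enter the general AE (later TEAE) tables by antibody status. Two limits apply. Protocol 8.3.6, on reporting laboratory deterioration, breaks off mid-sentence. Protocol Appendix A classes deterioration of the study disease from lack of effect as not reasonably caused by the drug, which would keep such events out of the table of AEs possibly caused by metreleptin. In any case, an AE table carries no HbA1c or triglyceride values.

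3. **Titer used for AEs.** Protocol 10.5: peak titer. SAP 17.1: apparently the last measurement before onset. The highest titer appears there only as a tie-break between events of the same type and severity. A last-prior titer cannot exceed the patient's own peak, so an event either stays in the peak stratum or falls in a lower one. Scheduled days by floor(month × 30.4) for Months 12, 18, 24, 30 and 36 are 364, 547, 729, 912 and 1094. The gaps are 183, 182, 183 and 182 days, so late in follow-up the last scheduled result can be about six months old.

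4. **Data available for the fix.** Protocol Table 1 schedules HbA1c, lipids and antibody samples together at Visits 3 to 12, which is 10 post-baseline visits. Paired patient-visits: at most 10 × 10 = 100 with the protocol's 10 patients, or 11 × 10 = 110 with the SAP's 11.

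5. **Size of the strata.** Protocol Table 5 expects 1 + 1 + 1 + 2 + 3 + 2 + 0 = 10 patients over the maximum-titer levels. Six levels are occupied, the largest holds 3 patients, and 3 of the 6 (titers 0, 5 and 25) hold one patient, for whom no SD exists. The SAP reports titers on a different dilution scale, so these counts are only indicative.

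**The case against.** The strongest reply is that reported loss of response is already linked to antibody status through protocol 8.3.8 and SAP 17.1. On that view, tables with one to three patients per stratum would be little more than listings, which SAP 8.1 already allows. The first part stands and narrows the point: what is missing is the laboratory values by stratum, not every link between response and antibodies. The second part bears on the format of the output. It does not explain why a planned analysis is left out undeclared.

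A reader might also draw stronger conclusions that the documents do not support:

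- **That the per-patient plot was dropped or made optional.** SAP 9 places the content of tables, listings and figures in a shell document that is not available here, and the SAP's as-needed wording concerns additional figures. All that can be said is that the visible SAP text does not name the plot.
- **That the protocol's summary of "titers, neutralizing activities detected by both methods, and any associated clinical events (i.e., loss of efficacy or AE) will be summarized" is a further omission.** SAP 15.2 and 17.1 largely cover it, and what remains is the same HbA1c and triglyceride gap.
- **That the last-prior rule is wrong.** It is defensible, because a whole-study peak may occur after the event. Its use as the stratifier is also an inference: the sentence directly serves the event-selection rule. The fault is that the difference is undeclared.
- **That most events change stratum.** With the peak at 4 to 7 months (protocol 10.2), (36 − 7)/36 = 81% to (36 − 4)/36 = 89% of follow-up lies after it. That is a share of calendar time, not of events. Protocol 2.1 speaks of a peak or plateau, and calls the time course in lipodystrophy less well defined. Neither document says how far titers fall.

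**Conclusion.** The point holds in a limited form. One protocol-planned analysis, HbA1c and triglyceride change by antibody status, is absent from the visible SAP, and SAP 4.3 is inaccurate in declaring no departure. The change from peak to last-prior titer in the AE tables is a secondary matter of declaration.

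The effect is confined to descriptive exploratory and safety outputs in 10 to 11 patients. The primary immunogenicity analysis is unaffected and no hypothesis test is involved. The documents do not allow a count of misplaced events or an estimate of harm.

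The conclusion assumes that the table shells and the parts of the change note that are not visible, including the changes made after database lock, do not restore these outputs. If they do, only the statement in SAP 4.3 remains to be corrected.

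**What to change.** - **SAP 18.2:** restore change in HbA1c and percent change in fasting triglycerides at each visit by peak ADA titer and by neutralizing category or percent inhibition. Use listings or patient profiles where a stratum holds one patient. The change note already postdates database lock, so label these outputs as protocol-planned but added after lock. The protocol sets no numerical threshold for loss of response; label any chosen now as post hoc.
- **SAP 4.3 (or the change note):** declare each departure, including last-prior in place of peak titer. Then either add the AE tables by peak titer or give the reason for the change.
- **Shells:** confirm that they contain the protocol's per-patient plot of titers, both neutralizing assays and exposure, and add it only if they do not.

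The cost is some wording, a few tables or listings and, if the plot is missing, 10 to 11 patient profiles. All use data already scheduled for collection. The results remain descriptive, some strata will be empty or hold one patient, and the after-lock label has to stay.
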